#### 4.5.6.3 *Laboratory data*

When result is '<x', value to be considered will be 'x-0.01'

When result is '>x', value to be considered will be 'x+0.01'

If after the following replacement a value become < 0 then value is forced to 0.

Baseline will be defined as the last available value before or the same day as first treatment intake.

Before first treatment intake, the last non-missing value before first intake will be selected.

After first treatment intake, in case of retest for a given parameter, the first non-missing value will be selected.

Regarding laboratory parameters that a sensitive to fasting status (Fasting Glucose, HOMA, insulin, C-peptid, Fructosamine, Triglycerides, Total cholesterol, HDL cholesterol, LDL cholesterol, Free fatty acids (FFA), Apoprotein A1, Apoprotein B, Apoprotein C3, Adiponectin, Leptin, FGF-21):

If the status is 'not fasting' and the value remains within laboratory ranges, then this value will be considered as 'fasting' for the analysis. This is applicable for the baseline value (See section 4.5.1) as well as all values collected over time.

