### 5.2.3 Blood samples taken

Blood sample taken are performed at every visit, i.e. V-1 (screening) to V4 (Follow-up). The patient must be fasting overnight from 10:00 pm. Alternatively, blood sampling can be performed in the afternoon provided patients have been fasting for at least eight hours. Total blood volume sampled during the study for each patient (for pharmacokinetics, biomarkers, safety and efficacy biological tests) will be as follows:

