#### 9.7.3 *Other Observations Related to Safety*

### - **Laboratory tests**

The analysis will include patients exposed to study medication who have at least one laboratory test performed after the first study product intake and, when required by the definition of the abnormality, with an available baseline value and available normal ranges. For these descriptions, the baseline value will be the latest available measure before the first study product dose intake. International units will be used in all listings, tables and graphs. Results and changes from baseline of laboratory parameters will be summarized by mean, standard deviation, median, minimum and maximum at each time point and for the final on-treatment visit. Unscheduled and/or repeated results will only be listed and not summarized.

Shift tables and other tabular and graphical methods will be used to present the results for tests of interest. Listings will be provided with flags indicating clinically significant out-of-range values, clinically non-significant out-of-range values.

In addition, out-of-range values will be assessed by the investigator as clinically significant or not clinically significant. Abnormal laboratory tests assessed by the investigator as clinically significant will be reported as an AE.

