#### 4.1.6 *Missing data*

##### 4.1.6.1 *General considerations*

Unless otherwise specified, missing data will not be replaced. In this case, the descriptive analyses of each variable will be based on the available data, i.e. Observed Cases (OC) analysis, considering missing data as non-informative. The number of missing data will be documented for each analysis.

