## 4.5 Derived variables

### 4.5.1 Baseline data and change from baseline

Baseline data will be considered as the last available non-missing data before or equal to the treatment start.

*Note: For biopsies, multiple reading rules (see section 4.5.4.1.1) should be applied before calculating Baseline values.*

Absolute change from baseline will be calculated as follows:

Value at  $V_i$  – Value at baseline, where  $i$  corresponds to a post-baseline value.

Relative change from baseline (in %) will be calculated as follows:

- if Value at baseline is not equal to 0:  $[(\text{Value at } V_i - \text{Value baseline}) / \text{Value at baseline}] * 100$ , where  $i$  corresponds to a post-baseline value.
- if both values at  $V_i$  and at baseline are equal to 0, then the relative change from baseline will be equal to 0%.

Regarding laboratory parameters that are sensitive to the fasting status (Fasting Glucose, HOMA, insulin, C-peptid, Fructosamine, Triglycerides, Total cholesterol, HDL cholesterol, LDL cholesterol, Free fatty acids (FFA), Apoprotein A1, Apoprotein B, Apoprotein C3, Adiponectin, Leptin, FGF-21):

- if the value at Baseline is a non-fasting value when the value at Screening is a fasting value, then the Baseline data will be the value at Screening
- if both values at Screening and Baseline are non-fasting values, then the Baseline data will be the value at Baseline.

Regarding laboratory parameters, the following status will be defined:

- Normal-Normal, if the baseline is within laboratory ranges and all values over time remain within laboratory ranges
- Normal-Abnormal, if the baseline is within laboratory ranges but at least one value over time is not within laboratory ranges
- Abnormal-Normal, if the baseline is not within laboratory ranges and all values over time are within laboratory ranges
- Abnormal-Abnormal, if the baseline is not within laboratory ranges and at least one value over time is not within laboratory ranges

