### 5.2.3.8 *Glucose metabolism*

#### **Main analysis**

The population of analysis will be the FAS as described in section 4.3.3. Only the observed cases under treatment will be analysed (see section 4.1.6.3).

Only fasting results will be considered for fasting glucose, insulin, C-peptid and HOMA index. HbA1c and fructosamide results will be considered regardless of the fasting status.

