## 5.2.3.10 Plasma lipids levels

The following table describes for each parameter the collection time and the type of analyses to be done.

Parameter	Collection time	Main analyses (see section 5.2.3.8 describing the methodology)	Sensitivity analyses	Subgroup analyses
Total Cholesterol	Screening, Baseline, weeks 4, 14, 24 and 28	Descriptive analysis Treatment effect ( each dose versus placebo ) Time course of the response of each treatment group	None	By diabetic status (Yes, No) By Statins at baseline (Yes, No)
HDL-C	Screening, Baseline, weeks 4, 14, 24 and 28	Descriptive analysis Treatment effect ( each dose versus placebo ) Time course of the response of each treatment group	None	By diabetic status (Yes, No) By Statins at baseline (Yes, No)
LDL-C	Screening, Baseline, weeks 4, 14, 24 and 28	Descriptive analysis Treatment effect ( each dose versus placebo ) Time course of the response of each treatment group	None	By diabetic status (Yes, No) By Statins at baseline (Yes, No)
Triglycerides	Screening, Baseline, weeks 4, 14, 24 and 28	Descriptive analysis Treatment effect ( each dose versus placebo ) Time course of the response of each treatment group	None	By diabetic status (Yes, No) By Statins at baseline (Yes, No)
Apo A1	Baseline, week 24	Descriptive analysis Treatment effect ( each dose versus placebo )	None	By diabetic status (Yes, No) By Statins at baseline (Yes, No)
FFA	Baseline, week 24	Descriptive analysis	None	By diabetic status (Yes, No) By Statins at baseline (Yes, No)
Adiponectin	Baseline, week 24	Descriptive analysis Treatment effect ( each dose versus placebo )	None	By diabetic status (Yes, No) By Statins at baseline (Yes, No)
Leptin	Baseline, week 24	Descriptive analysis	None	By diabetic status (Yes, No) By Statins at baseline (Yes, No)
APO B	Baseline, week 24	Descriptive analysis	None	By diabetic status (Yes, No) By Statins at baseline (Yes, No)

Parameter	Collection time	Main analyses (see section 5.2.3.8 describing the methodology)	Sensitivity analyses	Subgroup analyses
APO C3	Baseline, week 24	Descriptive analysis	None	By diabetic status (Yes, No) By Statins at baseline (Yes, No)
FGF21	Baseline, week 24	Descriptive analysis	None	By diabetic status (Yes, No) By Statins at baseline (Yes, No)

Only fasting results will be considered for analyses.

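### After baseline the SAP keeps the first of two repeated laboratory values without regard to fasting status, so a fasting repeat can be passed over in analyses restricted to fasting results

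*SAP*

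**What the plan says.** Four SAP rules meet on this point.

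- **Retest selection (SAP 4.5.6.3).** "After first treatment intake, in case of retest for a given parameter, the first non-missing value will be selected". No parameter is exempted, although the same section goes on to list the analytes that are sensitive to fasting.
- **Relabelling (SAP 4.5.6.3).** "If the status is 'not fasting' and the value remains within laboratory ranges, then this value will be considered as 'fasting' for the analysis". This applies to baseline and to all later values.
- **Fasting filter.** For glucose metabolism (SAP 5.2.3.8): "Only fasting results will be considered for fasting glucose, insulin, C-peptid and HOMA index". For lipids (SAP 5.2.3.10): "Only fasting results will be considered for analyses".
- **Missing values (SAP 4.1.6.1).** "Unless otherwise specified, missing data will not be replaced".

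At baseline the SAP does look at fasting status. SAP 4.5.1 substitutes the Screening value "if the value at Baseline is a non-fasting value when the value at Screening is a fasting value". Nothing equivalent exists after first intake.

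Protocol 5.2.3 requires every draw to be fasting: "The patient must be fasting overnight from 10:00 pm", or at least eight hours for afternoon sampling.

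**The concern.** The retest rule and the fasting restriction work against each other. The analysis wants a fasting result; the selection rule may set one aside because a non-fasting sample came first. The SAP accepts at baseline that fasting status outranks the order of the samples, but does not carry this forward. A change from baseline may then set a value chosen because it was fasting against a week 24 value that was not.

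The affected measures are protocol secondary endpoints: fasting glucose, insulin, HOMA, plasma lipids, apoA1 and adiponectin. Insulin, HOMA, apoA1 and adiponectin are measured after baseline only at week 24, so for them a lost value is a lost patient. Where a visit is lost, the loss depends on the first value being out of range. That sits poorly with SAP 4.1.6.1, which treats missing data as non-informative.

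**Working it through.** The plan states no figure to reproduce. The check is to run the written rules on one case: two samples at the same post-baseline visit, the first non-fasting and the repeat fasting, both within the on-treatment window. Two things vary: whether the first value is within the laboratory range, and which rule runs first.

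| Order of rules | First value in range | First value out of range |
|---|---|---|
| Retest selection, then fasting filter | Non-fasting first value analysed as fasting | Visit missing |
| Fasting filter, then retest selection | Non-fasting first value analysed as fasting | Fasting repeat used |

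1. *In range.* Relabelling makes the first value count as fasting, so it passes the filter and, being first, is selected. The order does not matter.
2. *Out of range, selection first.* The first value is selected, fails the filter and is not replaced. The visit is empty although a fasting result exists.
3. *Out of range, filter first.* Only the repeat survives the filter, and it is used.

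The fasting repeat is passed over in 3 of the 4 cells, and in both cells of the first row. That row is the literal reading, because retest selection sits under derived variables (SAP 4.5) and the filter under the analyses (SAP 5.2). The SAP does not state the sequence.

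**Illustration (invented values).** Week 24 triglycerides are 3.1 mmol/L non-fasting and 1.6 mmol/L on a fasting repeat the next day. Assume that 3.1 is out of range and that the last dose was no earlier than two days before the visit, so the repeat falls within 3 days of it. Selection first gives a missing week 24; filter first gives 1.6.

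**What is lost when a visit is missing:**

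| Analyte | Post-baseline visits (SAP 5.2.3.8, 5.2.3.10) | Loss |
|---|---|---|
| Insulin, HOMA, apoA1, adiponectin | Week 24 only | Patient leaves the treatment comparison |
| Fasting glucose, total cholesterol, HDL-C, LDL-C, triglycerides | Weeks 4, 14, 24, 28 | That visit only; the others stay in the MMRM |

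**After the change set out under the fix,** all four cells of the first table give the fasting repeat, because selection uses the recorded status and runs before the other two rules.

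**The case against.** **No passage describes a post-baseline repeat made because the patient was not fasting.** The defined retest visit belongs to screening (Protocol 5.3.2). Later extra draws serve safety (Protocol 5.3.7, 6.3, 6.3.2), and no repeat is described for insulin, apoA1 or adiponectin. This stands as a limit on how often the case arises. It does not remove the case: SAP 4.5.6.3 itself provides for retests after first intake and for non-fasting values over time.

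**The order is not stated.** This also stands. A reader might infer that the SAP certainly discards the visit; it does so only if selection precedes the filter. The in-range consequence needs no such assumption.

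**The in-range half comes from the relabelling rule.** Partly so. But removing relabelling alone would not settle the matter: with selection first, a non-fasting first value would then fail the filter whether or not it was in range. Fixing the order alone would leave the in-range case untouched.

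**The on-treatment window already excludes late repeats.** Correct. These analyses use observed cases under treatment, and SAP 4.1.6.3 sets aside non-biopsy data taken more than 3 days after last intake. A week 24 repeat outside that window is not a usable result that this rule throws away.

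**Taking the first value is conventional and guards against selective retesting.** It matches the ECG and vital-sign rules (SAP 4.5.6.4, 4.5.6.5), and Protocol 9.7.3 says of repeats: "Unscheduled and/or repeated results will only be listed and not summarized". That sentence concerns safety laboratory summaries, not fasting-only efficacy analyses. Choosing on recorded fasting status, never on the result, keeps the protection.

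**Conclusion.** The point holds as a small defect in a stated rule. An in-range non-fasting value displaces a true fasting repeat under either order of the rules. An out-of-range one empties the visit under the literal order.

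Three stronger readings are tempting and are not supported:

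- *That patients drop out of the glucose and lipid analyses generally.* This is true only of the tested measures with one post-baseline value. Glucose and the four main lipids lose a visit.
- *That the number affected can be estimated.* The documents give neither the share of non-fasting samples nor the share repeated. Any patient count would rest on two invented proportions. Since fasting is required at every draw, the number may be small.
- *That the treatment comparison is biased in a known direction.* The rule is the same in all arms, and nothing in the documents suggests that non-fasting attendance differs between them.

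The primary histological endpoint is untouched. The conclusion assumes only that at least one patient has a non-fasting sample followed by a fasting repeat at the same post-baseline visit, within the window.

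**What to change.** Add to SAP 4.5.6.3, for the analytes whose analysis is restricted to fasting results:

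- After first intake, select the first non-missing value whose recorded status is fasting, within the visit and the on-treatment window of SAP 4.1.6.3. Recorded status means the status before any in-range relabelling; otherwise a relabelled first value would still be chosen.
- If there is none, use the first non-missing value, still subject to the existing fasting rules.
- State that this selection runs before the relabelling and before the fasting filter.

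Keep the present rule for all other parameters. That includes HbA1c and fructosamine, which SAP 5.2.3.8 analyses whatever the fasting status.

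The cost is one sentence on selection, with the order stated, and a sort key in the derived laboratory dataset. No new data are needed. Stating the order also helps the double programming in SAP 4.1.3, where two programmers could otherwise build different datasets from the same text.

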Objectives/Endpoints	Type of analysis	Method of analysis	Population and imputation method
Glucose metabolism (fasting glucose, insulin, HOMA index, C-peptid, HbA1c and fructosamide)	Main analysis	Descriptive Treatment effect: MMRM or ANCOVA Time course: MMRM when possible	FAS – Observed Cases under treatment (considering only fasting values, when specified)
	Subgroups analysis (diabetic status) (HbA1c at for HbA1c)	Descriptive	FAS – Observed Cases under treatment (considering only fasting values, when specified)
Liver enzymes (ALT, AST, GGT, Alkaline Phosphatase, Total Bilirubin)	Main analysis	Descriptive Treatment effect: MMRM Time course: MMRM	FAS – Observed Cases under treatment
	Subgroup analysis (diabetic status)	Descriptive	FAS – Observed Cases under treatment
Plasma lipids levels (TC, HDL-C, LDL-C, TG, apoA1, FFA, Adiponectin, Leptin, APO B, APO C3 and FGF21)	Main analysis	Descriptive Treatment effect: MMRM or ANCOVA when specified Time course: MMRM when possible	FAS – Observed Cases under treatment considering only fasting values
	Subgroup analysis ; - diabetic status - statins at Baseline	Descriptive	FAS – Observed Cases under treatment considering only fasting values
Efficacy inflammatory markers (fibrinogen, hs- CRP, alpha2 macroglobulin, haptoglobin, IL-13, IL-17a, , IL-6, IL-1b, TNF-a, INFg)	Main analysis	Descriptive Treatment effect: ANCOVA when specified	FAS – Observed Cases under treatment

Objectives/Endpoints	Type of analysis	Method of analysis	Population and imputation method
Efficacy fibrosis markers (TIMP-1, TIMP-2, Hyaluronic acid, P3NP, NFS, FIB-4 score, ELF score, MACK-3, FIBC3, ABC3D, Cytokeratin M30, Cytokeratin M65, Liver iron content, MMP2, MMP9, Pro-C3)	Main analysis	Descriptive Treatment effect: ANCOVA when specified	FAS – Observed Cases under treatment
	Exploratory analysis	Cross-tabulation with the CRN-F score (F0-F1, F2-F3) when specified	FAS – Observed Cases under treatment
Efficacy chemistry markers (Plasma Iron, Transferrin, Ferritin)	Main analysis	Descriptive	FAS – Observed Cases under treatment

Subgroups of interest are :

(1)

- Biopsy length ( $\leq 8$ ,  $>8$  mm)
- SAF-A at Baseline (A2-A3, A4)
- CRN-F at Baseline (F0-F1, F2-F3)
- NAS score at baseline ( $<6$ ,  $\geq 6$ )
- BMI at Baseline (Obese, Non-Obese)Metabolic syndrome at Baseline (Yes, No)
- Insulin-resistance status at Baseline (Yes, No)
- Sex (Male, Female)

(2)

- NAS score at baseline ( $<6$ ,  $\geq 6$ )

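### A post-baseline non-fasting laboratory result enters the fasting glucose and lipid analyses only if it is in range, so inclusion depends on the outcome itself

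*SAP*

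**What the plan says.** SAP 4.5.6.3 lists 16 analytes as sensitive to fasting: glucose, HOMA, insulin, C-peptide, fructosamine, triglycerides, total, HDL and LDL cholesterol, free fatty acids, apolipoproteins A1, B and C3, adiponectin, leptin and FGF-21. If one of these is recorded as not fasting "and the value remains within laboratory ranges, then this value will be considered as" fasting. The scope is explicit: "This is applicable for the baseline value (See section 4.5.1) as well as all values collected over time".

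The analysis sections then filter on that label:

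- SAP 5.2.1, glucose metabolism: "Observed Cases under treatment (considering only fasting values", where specified.
- SAP 5.2.3.8: "Only fasting results will be considered for fasting glucose, insulin, C-peptid and HOMA index". One exemption follows: "HbA1c and fructosamide results will be considered regardless of the fasting status".
- SAP 5.2.3.10, for every analyte in the plasma lipids table: "Only fasting results will be considered for analyses".

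SAP 4.1.6.1 leaves missing values unreplaced and treats them as non-informative.

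Baseline has its own rule in SAP 4.5.1. Screening becomes the baseline "if the value at Baseline is a non-fasting value when the value at Screening is a fasting value". There is also a fallback: "if both values at Screening and Baseline are non-fasting values, then the Baseline data will be the value at Baseline". Neither provision applies after baseline.

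**The concern.** Whether a sample was fasting is a fact about how it was taken. Here the label is partly decided by the result, and the label decides whether the result is analysed. Selection on the measured value is informative by construction, contrary to SAP 4.1.6.1 and to the missing-at-random basis of the mixed model in SAP 4.1.5.

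Three things are at stake.

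- **Status tables.** In the Normal/Abnormal status-over-time tables (SAP 4.5.1 and 5.2.3.8), a post-baseline non-fasting sample can only ever count as normal.
- **Arm means and retention.** Retained non-fasting values are pulled into range. If treatment moves values across a limit, the share retained differs by arm. Protocol 1.5.2 selected the doses on adiponectin, HDL cholesterol and triglycerides, so movement in these analytes is expected. All three fall under the rule and are compared with placebo.
- **Baseline.** An in-range non-fasting V0 value counts as fasting and so displaces a genuinely fasting screening value, while an out-of-range one is replaced by the screening value.

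Nothing planned would reveal this. SAP 5.2.3.8 and 5.2.3.10 plan no sensitivity analysis for these analytes, and SAP 4.6 does not list the rule among the changes from the protocol.

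**Working it through.** **Which analytes are affected**

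- Of the 16 listed, fructosamine is exempt under SAP 5.2.3.8 (HbA1c is exempt too but is not on the list). That leaves 15.
- Nine are compared with placebo (SAP 5.2.3.8 and 5.2.3.10): glucose, insulin, HOMA, total, HDL and LDL cholesterol, triglycerides, apoA1 and adiponectin. The other six are descriptive: C-peptide, free fatty acids, leptin, apoB, apoC3 and FGF-21.
- Five have a screening sample (Protocol Table 8) and four post-baseline visits: glucose, triglycerides, and total, HDL and LDL cholesterol. Only these can show the baseline displacement.
- The other ten have one post-baseline sample, at week 24, which is the patient's whole post-baseline status.

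**What happens to a non-fasting result**

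| | In range | Out of range |
|---|---|---|
| After baseline | Relabelled fasting, analysed | Filtered out, not replaced |
| V0, fasting screening value exists | Used as baseline | Screening value used |
| V0, screening also non-fasting | Used as baseline | V0 kept by the fallback |

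No other passage rescues the top-right cell.

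**Size of the effect.** The documents give no non-fasting rate and no laboratory ranges, so every input below is an assumption. Let p be the non-fasting share, m the fasting mean, k the probability that a non-fasting value is in range, and c the mean of those in range. The arm mean under the rule is

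M = [(1-p)m + p·k·c] / [(1-p) + p·k].

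Values are taken as lognormal with σ² = ln(1+CV²) and μ = ln(mean) - σ²/2. With one upper limit U, k = Φ(z), where z = (ln U - μ)/σ, and k·c = mean × Φ(z - σ). A food effect multiplies the mean of non-fasting values.

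*Worked case:* triglycerides 1.9 (placebo) vs 1.5 (active) mmol/L, CV 45%, U = 1.7, p = 10%, no food effect. σ² = ln(1.2025) = 0.1844, so σ = 0.429.

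- Placebo: z = -0.044, k = 0.482, c = 1.252. M = (0.9×1.9 + 0.1×0.482×1.252)/(0.9 + 0.0482) = 1.867.
- Active: z = 0.506, k = 0.694, c = 1.147. M = (0.9×1.5 + 0.1×0.694×1.147)/(0.9 + 0.0694) = 1.475.
- The difference is 0.392 against a true 0.400 (-1.9%). The rule keeps 48% of non-fasting values on placebo and 69% on active. With a +20% food effect it keeps 32% and 53%.

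*All scenarios at p = 10%* (glucose CV 20%, HDL CV 25%; food effect +20% for triglycerides, +15% for glucose):

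| Scenario, mmol/L (range) | True difference | No food effect | With food effect |
|---|---|---|---|
| Triglycerides 1.9 vs 1.5 (≤1.7) | 0.400 | 0.392 | 0.395 |
| Triglycerides 2.6 vs 2.2 (≤1.7) | 0.400 | 0.404 | 0.404 |
| Glucose 6.2 vs 5.4 (3.9-5.6) | 0.800 | 0.790 | 0.799 |
| Glucose 6.2 vs 5.4 (3.9-6.1) | 0.800 | 0.777 | 0.787 |
| Glucose 7.2 vs 6.4 (3.9-5.6) | 0.800 | 0.814 | 0.807 |
| HDL 1.15 vs 1.30 (≥1.0) | -0.150 | -0.147 | not run |

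*Over other non-fasting rates:*

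| Non-fasting share | Change in treatment difference, all scenarios | Abnormal share understated, single sample |
|---|---|---|
| 2% | -0.5% to +0.3% | 0.5 points |
| 5% | -1.4% to +0.8% | 1.3 points |
| 10% | -2.9% to +1.7% | 2.6 points |
| 20% | -6.2% to +3.5% | 5.6 points |

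The last column is A - (1-p)A/[(1-p) + p·k] with A = k = 0.5. At 10% this is 0.5 - 0.45/0.95 = 0.026.

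*Other checks:*

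- No treatment effect and equal non-fasting rates: no shift in the difference.
- No treatment effect but unequal rates (5 vs 2%, 10 vs 5%, 20 vs 10%), triglyceride mean 1.9: shifts of -0.010, -0.017 and -0.037 mmol/L.
- Four post-baseline visits (simulation of 400,000 patients, within-patient correlation 0.6, 20% non-fasting): Normal-Normal is 44.85% under the rule and 44.76% using fasting samples only.
- A separate glucose simulation (placebo mean 6.3, SD 1.2, true difference -1.0, food effect about +1.0 mmol/L, upper limit 5.6 or 6.1) gave -0.97 to -0.99 at 20% non-fasting, and essentially no change at 2%.

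**The case against.** The strongest case against concerns weight, not the reading of the text.

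- **Few samples.** Protocol 5.2.3 requires fasting. With 247 randomised (SAP 3.5), about 82 per arm, an assumed 5% rate gives about four non-fasting samples per arm per visit. If half are out of range, about two are dropped. This stands, and it is why the point is moderate.
- **The extremes need no food effect.** With the assumed +15% effect, the two glucose scenarios that set the 20% bounds give -3.7% and +2.0% instead of -6.2% and +3.5%. This also stands.
- **The rule has a rationale.** Where food raises a value, an in-range fed result implies that the fasting value is also below the upper limit. That supports a normal label on that side. It does not make a fed value a fasting measurement in a change-from-baseline model, and it does not carry over to HDL, where the lower limit matters.
- **Ranges may not exist for every analyte.** HOMA has only a cut at 3 in SAP 4.5.4.3. Without a range the relabelling cannot operate, so the analyte counts are upper limits in that sense. However, SAP 5.2.3.8 plans a normal/abnormal status for HOMA and the other glucose analytes, and SAP 5.2.3.10 refers to that methodology for the lipids. The plan therefore presumes ranges.
- **Baseline displacement cannot systematically favour an arm,** since both candidate values precede dosing. Agreed; it adds error and undercuts the purpose of SAP 4.5.1.
- **Low decision weight.** The primary endpoint is histological. Protocol 9.7.4 puts the glucose, lipid and adiponectin comparisons under exploratory analyses, although Protocol 9.1 names them as secondary endpoints. The rule is also prespecified and the same in all arms. None of this removes the selection on outcome.

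**Conclusion.** The concern holds. As written, the SAP keeps or drops a post-baseline non-fasting result according to its value, for up to 15 analytes, nine of them compared with placebo. The effect on treatment differences is probably small and can go in either direction. The clearest distortion is in the status tables for the ten analytes sampled once after baseline. With four post-baseline visits the patient-level status changes by less than 0.1 point. All sizes rest on assumed non-fasting rates, distributions, limits and food effects, and the true size cannot be derived from the documents. The primary endpoint is unaffected. The rule should be corrected because it selects on the outcome and the remedy is cheap, not because a large bias has been shown.

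**What to change.** 1. In SAP 4.5.6.3, delete the sentence that relabels in-range non-fasting values and the sentence that extends it to baseline and all later values. Recorded fasting status alone then decides which post-baseline values are analysed and whether screening or V0 is the baseline.
2. Keep the SAP 4.5.1 fallback to the V0 value. State that it also covers analytes with no screening sample and that it overrides the fasting-only filter, and flag the patients concerned. Do not set baseline to missing, because the change-from-baseline models in SAP 4.1.5 need it.
3. Add one sensitivity analysis using all values regardless of fasting status.
4. State whether a fasting retest replaces a non-fasting first result. SAP 4.5.6.3 currently takes the first non-missing value after first intake, which affects how many values are lost.

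The cost is SAP wording, one extra analysis, and the loss of in-range non-fasting post-baseline values from the main analysis; the sensitivity analysis still uses them. No patient loses a baseline.
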